4.9 Changes in the planned analysis

No change has been implemented in this SAP.

However, in order to clarify the analysis of the primary endpoint, a clarification of the meaning of "supplemental oxygen treatment" is provided: since all patients enrolled in this study had a respiratory distress, it is intended in all the analysis that the term "supplemental" refers to additional and/or increased oxygen requirement as compared to the baseline. In fact, all patients were expected to be already on oxygen treatment before the start of treatment. Details are provided in section 9.1.

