# 9 STATISTICAL CONSIDERATIONS

#### 9.1 Sample size

The sample size for this trial will be adaptively determined through a phase 2/3 design. Enrollment is planned to last approximately 2 months. Each patient will be randomly allocated to Reparixin or Control according to a randomization ratio of 2:1 and he/she will be followed for the entire treatment and follow-up duration for collecting the efficacy endpoints of each study phase.

For the Phase 2 portion of the study, the primary analysis will compare Reparixin versus Control in terms of time to a composite endpoint (primary endpoint of phase 2) including the following events: requirement of supplemental oxygen treatment, mechanical ventilation use, admission to ICU, and any requirement of rescue medication. Based on clinical experience, an improvement of the median time freedom from composite event of 1.5 times is expected. Assuming an exponential distribution, a total sample size of 48 patients will allow to provide 80% power to show superiority of Reparixin compared to control using a log-rank test at a one-sided significance level of 0.025.

The sample size for the phase 3 is based on assessment of superiority of Reparixin compared to control arm in terms of freedom from a composite endpoint (primary endpoint of phase 3) of severe events including death, admission to the ICU, requirement of mechanical ventilation.

Based on same assumptions of phase 2 regarding randomization (2:1) and expecting to double the median time freedom from severe composite event using Reparixin compared to control (from 2-4 to 4-8 days), a total sample size of 111 patients will allow to achieve a power of 90% to show superiority of Reparixin over control using a log-rank test at a one-sided significance level of 0.025. No drop-out are expected to happen. The number of patients to be included may be revised based on considerations from Phase 2 data analysis.

Primary endpoint of phase 3 will be tested only if superiority of Reparixin is shown in phase 2. Thus, the overall type I error of the study will be controlled at 0.025 via the hierarchical testing procedure.

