3.5 Efficacy endpoints

3.5.1 Primary endpoints

- Primary Endpoint for phase 2: Composite endpoint of clinical events (the subject requires at least one of the following: supplemental oxygen requirement, invasive mechanical ventilation use, admission to ICU, and use of a rescue medication for any reason);
- Primary Endpoint for phase 3: Composite endpoint of death and clinical severe events (the subject dies or requires invasive mechanical ventilation use and/or admission to ICU).

3.5.2 Secondary Endpoints:

- Clinical severity score (a seven-category ordinal scale) at any available time point
- Dyspnea severity (Liker categorical scale and VAS continuous scale) at any available time point;
- Changes in body temperature at any available time point;
- Duration and quantity of supplemental oxygen treatment at any available time point;
- Incidence and duration of mechanical ventilation use at any available time point;
- Incidence of ICU admission need at any available time point;
- Lung damage extension changes from baseline (assessed by Chest CT or Rx) at any available time point;
- Change from baseline in lung exudation degree (assessed by Chest CT or Rx) at any available time point;
- PaO₂ at any available time point;
- SpO₂ at any available time point;
- Partial arteriolar oxygen pressure (PaO₂) to fraction of inspiration O₂ (FiO₂) ratio at any available time point;
- CRP at any available time point;
- Hs-CRP at any available time point;

3.5.3 Exploratory Endpoints (not mandatory):

- Cytokine profile at any available time point;

- Concentration of reparixin in serum over time;
- SARS-CoV-2 virologic counts at any available time point.

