9.1 Variable derivation

Table 7: Variable derivation rules

Parameter	Derivation
ARDS Severity classification based on PaO₂/FiO₂	
According to PaO₂/FiO₂ (RESPIRATORY PARAMETERS form) the classification is:
 
 • if $200 \leq \text{PaO}_2/\text{FiO}_2 < 300$ mmHg then ARDS Severity=Mild • if $100 \leq \text{PaO}_2/\text{FiO}_2 < 200$ mmHg then ARDS Severity=Moderate • if $\text{PaO}_2/\text{FiO}_2 < 100$ mmHg then ARDS Severity=Severe
Worsening based on PaO₂/FiO₂	
A patient with ARDS ($\text{PaO}_2/\text{FiO}_2 < 300$ mmHg) is considered “Worsened” in case of a decrease of PaO₂/FiO₂ of at least one third (-33,3%) from the baseline PaO₂/FiO₂ value.

Oxygen Delivery System Classification based on type of oxygen support	
According to Type of oxygen support (RESPIRATORY PARAMETERS form) the classification is:
 
 • If “Invasive Medicinal Ventilation” or “ECMO” then Class=Invasive • Else if “High Flow Nasal Cannula” or “BIPAP or CPAP” then Class=High Flow • Else if “Nasal Cannula” or “Mask” then Class=Low Flow
Worsening based on Oxygen Delivery System Classification	
A patient is considered “Worsened” after baseline if he/she increase the level of severity within the oxygen delivery system classification (Invasive > High Flow > Low Flow).

Last available date (for censoring time-to-event analysis)	
Last date will be considered as the most recent dates collect in:
 
 • Last assessment, • Start and stop dates of AEs 
Last date = max (date of last assessment, start AEs, Stop AEs)

Parameter	Derivation

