Time to supplemental oxygen requirement (days)	Time to supplemental oxygen requirement (days) = First Administration start date - Date of randomization
Time to mechanical invasive ventilation use (days)	Time to (invasive) mechanical ventilation use (days) = First (invasive) Mechanical Ventilation start date - Date of randomization
Time to admission to ICU (days)	Time to admission to ICU (days) = Admission date - Date of randomization
Time to rescue medication (days)	Time to rescue medication (days) = First rescue treatment start date - Date of randomization
Overall survival (days)	Overall survival (days) = Date of death - Date of randomization
Subject with improvement based on Likert scale	Improvement = any of these answers: 
 • 1 = minimally better, • 2 = moderately better, and • 3 = markedly better
Cumulative quantity (L) of oxygen treatment	Cumulative quantity of oxygen treatment (L) = Sum of all Quantity (L) in CONCOMITANT OXYGEN TREATMENT form, from randomization to time point of interest. It is defined as supplemental oxygen requirement any increased used of oxygen compared to baseline.
Cumulative duration (hours) of oxygen treatment	Cumulative duration of oxygen treatment (hours) = Sum of duration of oxygen administration (hours) in CONCOMITANT OXYGEN TREATMENT form, from randomization to time point of interest. Duration of oxygen administration (hours) = Administration end date/time - Administration start date/time / 60
Cumulative duration (hours) of mechanical ventilation	Cumulative duration of mechanical ventilation (hours) = Sum of duration of mechanical ventilation (hours) in MECHANICAL VENTILATION form, from randomization to time point of interest. Duration of mechanical ventilation (hours) = End date/time - Start date/time / 60
Duration (days) of ICU stay	Duration of ICU stay (days) = Discharge date - Admission date
Change from baseline	For changes from baseline the baseline value will constitute the minuend and the later value the subtrahend.
Conversion of Time Intervals	If a time interval was calculated in minutes, hours or days and needs to be converted into months or years the following conversion factors will be used: 
 • 1 hour = 60 minutes • 1 day = 24 hours • 1 week = 7 days • 1 month = 30.4375 days • 1 year = 365.25 days

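### SAP 4.9 defines the supplemental oxygen component as increased oxygen need, but Table 7 derives it from a one-third fall in PaO2/FiO2 and dates the single-component analysis by a third rule

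*SAP*

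**What the plan says.** **Protocol.** Section 9.1 lists the phase 2 composite as "requirement of supplemental oxygen treatment, mechanical ventilation use, admission to ICU, and any requirement of rescue medication". Sections 3 and 9.4.2.1 are similar. None compares oxygen with baseline or sets a PaO2/FiO2 threshold.

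**SAP 3.5.1.** The composite is "supplemental oxygen requirement, invasive mechanical ventilation use, admission to ICU, and use of a rescue medication for any reason". The oxygen term is again undefined. (The restriction to invasive ventilation is a separate matter.)

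**SAP 4.9.** The section opens with "No change has been implemented in this SAP". It then clarifies that, in all analyses, the term "refers to additional and/or increased oxygen requirement as compared to the baseline", because "all patients were expected to be already on oxygen treatment before the start of treatment". It closes with "Details are provided in section 9.1".

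**SAP 9.1, Table 7.** Four entries bear on the component:
- The primary composite takes component 4 from the PaO2/FiO2 worsening rule, a decrease "of at least one third (-33,3%) from the baseline" value in a patient whose ratio is below 300 mmHg. The event is dated at the visit, and only post-baseline components count.
- The single-component row reads "Time to supplemental oxygen requirement (days) = First Administration start date - Date of randomization".
- The cumulative oxygen quantity row repeats the 4.9 meaning: any use above baseline.
- A second version of the composite uses a step up in oxygen delivery class. SAP 7.2.2.1 places it among the secondary analyses.

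**SAP 7.1.3.1.** First supplemental oxygen requirement is to be analysed on its own as a sensitivity analysis. The decision to proceed to phase 3 rests on the primary analysis alone.

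**The concern.** One named component carries a stated meaning, a derivation in the primary composite and a derivation in the component analysis, and the three do not identify the same event. A reader of 4.9 would take the composite to count patients who needed more oxygen; the analysis will count patients whose gas exchange fell by a third. The component analysis is meant to show what drives the composite, but it would describe a different event, and for many patients it could yield times that a survival analysis cannot use. The one-third threshold is also absent from the protocol and from the section that lists changes. In an open-label trial, a reader will want to know when it was chosen.

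**Working it through.** **The plan's own figure.** SAP 3.2 plans 46 events from about 48 subjects with approximately 80% power. The inputs are Table 2 (2 versus 5 days, read as exponential medians), 21 days of follow-up and 2:1 allocation (16 control, 32 reparixin).

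Expected events = 16 × (1 − 2^(−21/2)) + 32 × (1 − 2^(−21/5)) = 16 × 0.9993 + 32 × 0.9456 = 46.2.

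At a hazard ratio of 2/5 = 0.40, power with the SAP Table 4 efficacy and futility boundaries is 80.1%. Both figures reproduce. They depend on the assumed event times, not on how the oxygen component is defined, so they do not settle this point.

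**Does the PaO2/FiO2 rule match increased oxygen need?** The rule fires when (later ratio − baseline ratio) / baseline ratio ≤ −1/3. At constant PaO2 the ratio is proportional to 1/FiO2, so FiO2 must rise by a factor of 1/(1 − 1/3) = 1.5 before it fires. All PaO2 and FiO2 values below are assumed for illustration.

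| Baseline | Later | Ratio | Change | More oxygen than baseline? | Component 4 event? |
|---|---|---|---|---|---|
| 75 on 0.30 | 75 on 0.40 | 250 to 187.5 | -25% | Yes | No |
| 60 on 0.21 (room air) | 60 on 0.30 | 286 to 200 | -30% | Yes, newly started | No |
| 80 on 0.40 | 90 on 0.60 | 200 to 150 | -25% | Yes | No |
| 90 on 0.40 | 59 on 0.40 | 225 to 147.5 | -34% | No | Yes |

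The two definitions disagree in both directions. The room-air case can arise because one of the alternative entry criteria is a respiratory rate of at least 30 without oxygen.

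**Does the single-component row match either definition?** The row subtracts the randomization date from the start date of the first administration. It does not require that the administration be after baseline or exceed baseline use. For a patient on oxygen before treatment, the start date read literally is on or before randomization, so the time is zero or negative. Component 4 is dated at the visit where the ratio has fallen, so the row differs from it in both event and date.

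**What does 4.9 disclose?** It states the baseline-relative reading and points to 9.1. It does not mention PaO2/FiO2 or the one-third threshold, and neither is in the protocol's definition.

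**The case against.** The primary composite has one operational rule. Table 7 fixes the component, restricts it to post-baseline events and dates it. Section 4.9 is a short statement of meaning that defers to 9.1, and SAP 7.2.2.5 openly analyses supplemental oxygen by PaO2/FiO2 and by delivery class. This stands: the primary test can be run without ambiguity.

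The start-date row can be read charitably. If supplemental always means above baseline, the first administration could be the first increased one. The case report form, which would show what the start date records, is not available here, and some patients may enter without oxygen. This stands in part: the row need not fail for everyone, but it does not state the charitable reading, and even that reading would differ from component 4.

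A reader might infer that the go/no-go result is undermined. The documents do not support that. The start-date row feeds only a sensitivity analysis, which 7.1.3.1 keeps out of the decision, and the decision itself uses a single specified rule.

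A reader might also infer a concealed or data-driven change, since the SAP is dated 29 November 2020, against a protocol of 23 April 2020, and writes of enrolled patients in the past tense. Protocol 9.4.1 allows the SAP at any time before database lock, SAP 4.5 assigns the interim analyses to the DMC, 4.9 discloses the baseline-relative reading, and nothing shows that data by arm had been seen. What remains is that the threshold is not disclosed as an addition.

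**Conclusion.** The point holds as a mismatch between stated meaning and derivation, together with a component date that is unusable or mismatched if followed as written. It should be fixed, but it does not invalidate the phase 2 test. The illustrations show that disagreement is possible in both directions, not how often it would occur. The documents give no event rate under any of the oxygen definitions, so the effect on event count or power cannot be quantified. The finding of zero or negative times rests on a literal reading of the start-date row and on the SAP's own expectation that all patients were already on oxygen.

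**What to change.** 1. In Table 7, derive time to supplemental oxygen requirement from the same post-baseline component 4 event date that the primary composite uses.
2. Reconcile 4.9 with Table 7. At the least, state in 4.9 that the component is operationalised as a one-third fall in PaO2/FiO2 from baseline, and name the delivery-system composite in 7.2.2.1 as the alternative already planned. Whether that composite is called secondary or sensitivity is a matter of preference.
3. Replace the no-change sentence with a statement that the baseline-relative reading and the PaO2/FiO2 threshold are additions to the protocol's definition, and say whether both were set before any data by arm were reviewed.

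The cost is one derivation row and a few sentences in 4.9. The primary test, boundaries and sample size stay as they are. Both oxygen rules are already specified in Table 7; the documents do not show whether either has been programmed. Rewriting component 4 to match 4.9 would cost more: it would alter the primary composite and the version that adds death, and could make the delivery-system version redundant.

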4.10 Data Review Meeting

A DRM will be held before final database lock.

4.11 Software

All statistical analyses and data processing will be performed using Statistical Analysis Systems (SAS[®]) Software (release 9.4 or later).

5. Evaluation of Demographic and Baseline Characteristics

5.1 Subject enrolment and disposition

All presentations for subject disposition will be by treatment group, and overall.

For describing the subject disposition, the following populations will be summarized:

- Subjects enrolled (overall);
- Subjects enrolled but not randomized and reasons for non-allocation (overall);
- Subjects randomized;
- Subjects in each analysis set (FAS, SAF, PP) and reasons for exclusion;

For the overall report, the percentage denominator will be the number of ENR subjects. For the “by treatment group” calculations, the percentage denominator will be the number of randomized subjects within each arm.

Listings will be provided based on ENR set.

5.2 Protocol violations

All the protocol violations will be discussed case by case with the clinical team during the DRM and described in the DRM Report.

Number of occurrences and of subjects with at least one major and minor protocol violations will be summarized for each treatment.

5.3 Study discontinuations

The following information will be summarized by treatment and overall:

- Trial completers;
- Subjects who discontinued the IMP (and reasons);
- Subjects who discontinued the trial prematurely (and reasons);
- Subjects who discontinued the IMP but complete the study;
- Subjects who discontinued the IMP and discontinued the trial prematurely.

If more than 30% of randomized subjects discontinue the study prematurely, the distribution of the time from randomization to discontinuation will be summarized using time-to-event method. Subjects who have not prematurely discontinued the trial will be censored at study termination.

5.4 Patient status

The following information will be summarized by treatment at each time point:

- Subjects continuing treatment with oral reparixin/standard of care (yes, no, NA);
- Subjects switching to rescue medication (yes, no, NA);
- Subjects continuing treatment with IV reparixin (yes, no, NA), if applicable;

5.5 Demographics and baseline characteristics

The baseline demographic characteristics will be summarized by treatment and overall, by means of descriptive statistics. No statistical testing will be carried out for demographic or other baseline characteristics.

The following demographic and baseline characteristics will be reported:

- Demography
- Age (years)
- Gender (Male, Female)
 - If female, potential childbearing (yes, no)
- Race (White / Caucasian, Black or African American, Asian, Other)
- Ethnicity (Hispanic or Latino, Not Hispanic or Latino, Unknown, Not Reported)
- Pregnancy test result (Positive or Negative), if appropriate

5.6 Medical/Surgical History and Concomitant Diseases

A disease is considered as medical/surgical history if it is ended before screening visit. A disease is considered as concomitant disease if it is ongoing at screening visit.

Medical history and concomitant diseases will be coded using Medical Dictionary for regulatory activities (MedDRA) dictionary and frequency distributions and percentages will be summarized by treatment, by System Organ Class (SOC), and Preferred Term (PT).

Medical history and concomitant diseases will be analyzed separately. Frequency distributions and percentages by treatment will be given for both SOC and PT by subject. Subjects experiencing more than one past/concomitant disease event will be counted only once within each SOC and PT.

5.7 Prior and concomitant medications

Medications will be coded using World Health Organization Drug Dictionary (WHO DD).

Prior medications are those which stop prior to the date of informed consent. Concomitant medications are those which:

- start prior to, on or after the date of informed consent and start no later than date of study completion or discontinuation, and
- end on or after the date of informed consent or are ongoing at the study completion or discontinuation.

In case of missing or incomplete dates/times not directly allowing allocation to any of the two categories of medications, a worst-case allocation will be done according to the available parts of the start and the end dates (see Table 9). The medication will be allocated to the first category allowed by the available data, according to the following order:

- concomitant medication;
- prior medication.

Prior and concomitant medications will be summarized separately. Frequency distributions and percentages by treatment will be given by Anatomical Main Group (1st level of the Anatomical Therapeutic Chemical (ATC) classification), Chemical Subgroup (4th level of the ATC classification) and Preferred Name.

Subjects experiencing more than one medication classified in the same category (prior medications or concomitant medications) within the same anatomical main group, chemical subgroup and preferred name will be counted only once.

5.8 Other baseline characteristics

The following information at baseline will be descriptively reported by means summary statistics:

- Clinical severity score (categorical)
- Dyspnea VAS scale (continuous)
- Respiratory parameters (continuous)
 - FiO₂ (%)
 - Respiration rate (Breath/min)
 - PaO₂ (mmHg)
 - SpO₂ (%)
 - PaO₂/FiO₂ (Ratio)
 - Acute Respiratory Distress Syndrome (ARDS) severity and their categorical evaluation, if applicable.
- Additional information
 - Did the subject experience any Adverse Events? (yes, no);
 - Has the subject been admitted to the ICU? (yes, no);
 - Was oxygen administered to the subject? (yes, no);
 - Has the subject been mechanically ventilated? (yes, no).

6. Evaluation of Treatment Compliance and Exposure

6.1 Treatment information

Descriptive analyses of the following parameters will be presented at each available time point:

- For subjects treated with oral reparixin:
 - Total number of oral treatment days
 - Total n° oral tablets administered
- For subjects treated with standard of care:
 - Total number of oral treatment days
- For subjects treated with IV reparixin (if applicable):
 - Total number of IV treatment days

- Total n° IV Vials administered

6.2 Exposure to IMP

The extent of exposure to IMP in days will be summarized with descriptive statistics by treatment group. The extent of exposure (days) will be calculated using the formula reported in Table 7.

7. Evaluation of Efficacy

As described in section 0, possible modifications in the phase 3 study might be introduced as adaptation from phase 2. In this case, all the impacted below sections will be amended.

7.1 Analysis of primary efficacy endpoints

7.1.1 Testing strategy and multiplicity adjustment

7.1.1.1 Phase 2

The following null hypothesis is defined: the freedom from composite endpoint (section 3.5.1) in reparixin is lower or equal than control:

$$H_0: T_{\text{REPARIXIN}} \leq T_{\text{CONTROL}}$$

$$H_1: T_{\text{REPARIXIN}} > T_{\text{CONTROL}}$$

where $T_{\text{REPARIXIN}}$ and T_{CONTROL} are the freedoms from composite endpoint for reparixin and standard of care, respectively. The null hypothesis H_0 will be rejected, and preliminary (to be confirmed in phase 3) superiority of reparixin shown if log-rank p-value will be lower than pre-specified threshold, depending at which analysis (interim or final) the test is performed. Thresholds are calculated according to O'Brien-Fleming spending function boundaries and are reported in Table 4.

7.1.1.2 Phase 3

The following null hypothesis is defined: that the freedom from severe composite endpoint (section 3.5.1) in reparixin is lower or equal than control:

$$H_0: \Pi_{\text{REPARIXIN}} \leq \Pi_{\text{CONTROL}}$$

$$H_1: \Pi_{\text{REPARIXIN}} > \Pi_{\text{CONTROL}}$$

where $\Pi_{\text{REPARIXIN}}$ and Π_{CONTROL} are the freedoms from severe composite endpoint for reparixin and standard of care, respectively. The null hypothesis will be rejected, and superiority of reparixin concluded if log-rank p-value will be lower than pre-specified threshold, depending at which analysis (first or second interim or final) the test is performed. Thresholds are calculated according to O'Brien-Fleming spending function boundaries and are reported in Table 5.

Phase 3 null and alternative hypotheses will be tested only if superiority of reparixin is shown in phase 2. Null hypotheses of both phases must be rejected in order to claim superiority of reparixin over standard of care. Consequently, no multiplicity correction of type I error will be applied on primary analyses.

